### 5.4 Treatment Modification Guidelines for Infusion-Related Reactions

Please see the below table for suggested treatment modification for symptoms of infusion related reactions

NCI-CTCAE Grade (modified)	Treatment Modification for Study Drug
Grade 1 – mild Mild transient reaction; (based on combination of signs and symptoms which may include mild pruritus, flushing, rhinitis, rash, fever, and chills)	Stop study drug infusion and provide supportive care in accordance with local institutional hypersensitivity protocol. Resume infusion at 50% of previous rate once acute infusion-related reaction has resolved and monitor closely for any worsening.
Grade 2 – moderate Therapy or infusion interruption indicated but responds promptly to symptomatic treatment (for example, antihistamines,	Stop study drug infusion and provide supportive care in accordance with local institutional hypersensitivity protocol.

NSAIDs, narcotics, IV fluids); prophylactic medications indicated for ≤ 24 h.
	
Resume infusion at 50% of previous rate once infusion-related reaction has resolved or decreased to at least Grade 1 in severity, and monitor closely for any worsening.

Grade 3 or Grade 4 – severe or life-threatening                  Grade 3: Prolonged (for example, not rapidly responsive to symptomatic medication and/or brief interruption of infusion); recurrence of symptoms following initial improvement; hospitalization indicated for clinical sequelae.                  Grade 4: Life-threatening consequences; urgent intervention indicated.
	
Stop the study drug infusion immediately and disconnect infusion tubing from the subject.                  Subjects have to be withdrawn immediately from study drug treatment and must not receive any further study drug treatment.


 
• If hypersensitivity reaction occurs, the subject must be treated according to the best available medical practice.
 
• Once the avelumab infusion rate has been decreased by 50% or interrupted due to an infusion-related reaction (grade 1 or 2), the infusion rate may be increased back to the initial rate during that same infusion or during subsequent infusions at the discretion of the provider. Subjects may also be pre-medicated with steroids and/or oral or inhaled cromolyn sodium at the discretion of the provider.
 
• For subsequent infusions after a grade 1 or 2 reaction, at least 1 modification must be made to the infusion parameters: rate can be decreased (to a 3 or 4 hour infusion) and/or additional pre-medications can be administered at the discretion of the provider.
 
• The starting infusion rate for the study drug should not exceed 4 hours.
 
• If the avelumab is given over 4 hours, the options for optimization of pre-medications have been exhausted, and the patient continues to experience a grade 1 or 2 reaction, then the study drug must be discontinued permanently.
 
	

## 5.5 Management of Immune-mediated Adverse Reactions

Please see the table below for management of immune-mediated adverse reactions

Since inhibition of PD-L1 stimulates the immune system, immune-related AEs (irAEs) may occur. Treatment of irAEs is mainly dependent upon severity (NCI-CTCAE grade):                  Grade 1 to 2: treat symptomatically or with moderate dose steroids, more frequent monitoring                  Grade 1 to 2 (persistent): manage similar to high grade AE (Grade 3 to 4)                  Grade 3 to 4: treat with high dose corticosteroids                  Treatment of gastrointestinal, dermatological, pulmonary, hepatic and endocrine irAEs should follow guidelines set forth in the table below.
		

Gastrointestinal irAEs
		

Severity of Diarrhea / Colitis (NCI-CTCAE v4.03)
	
Management
	
Follow-up

Grade 1 Diarrhea: < 4 stools/day over Baseline Colitis: asymptomatic
	
Continue avelumab therapy Symptomatic treatment (for example, loperamide)
	
Close monitoring for worsening symptoms Educate subject to report worsening immediately If worsens: Treat as Grade 2 or 3/4

Grade 2 Diarrhea: 4 to 6 stools per day over Baseline; IV fluids indicated < 24 hours; not interfering with ADL Colitis: abdominal pain; blood in stool
	
Delay avelumab therapy Symptomatic treatment
	
If improves to Grade 1: Resume avelumab therapy If persists > 5 to 7 days or recur: 0.5 to 1.0 mg/kg/day methylprednisolone or equivalent When symptoms improve to Grade 1, taper steroids over at least 1 month, consider prophylactic antibiotics for opportunistic infections, and resume avelumab therapy per protocol (if reduced to 10 mg/day or less of prednisone equivalent). If worsens or persists > 3 to 5 days with oral steroids: Treat as Grade 3 to 4


Grade 3 to 4 Diarrhea (Grade 3): ≥ 7 stools per day over Baseline; incontinence; IV fluids ≥ 24 hrs.; interfering with ADL Colitis (Grade 3): severe abdominal pain, medical intervention indicated, peritoneal signs Grade 4: life-threatening, perforation
	
Discontinue avelumab therapy per protocol 1.0 to 2.0 mg/kg/day methylprednisolone IV or equivalent Add prophylactic antibiotics for opportunistic infections Consider lower endoscopy
	
If improves: Continue steroids until Grade 1, then taper over at least 1 month If persists > 3 to 5 days, or recurs after improvement: Add infliximab 5 mg/kg (if no contraindication), Note: Infliximab should not be used in cases of perforation or sepsis

Dermatological irAEs
		

Grade of Rash (NCI-CTCAE v4)
	
Management
	
Follow-up

Grade 1 to 2 Covering ≤ 30% body surface area
	
Symptomatic therapy (for example, antihistamines, topical steroids) Continue avelumab therapy
	
If persists > 1 to 2 weeks or recurs: Consider skin biopsy Delay avelumab therapy Consider 0.5 to 1.0 mg/kg/day methylprednisolone IV or oral equivalent. Once improving, taper steroids over at least 1 month, consider prophylactic antibiotics for opportunistic infections, and resume avelumab therapy once patient has reached prednisone equivalent of 10 mg/d and improving. If worsens: Treat as Grade 3 to 4

Grade 3 to 4 Covering > 30% body surface area; life threatening consequences
	
Delay or discontinue avelumab therapy Consider skin biopsy Dermatology consult 1.0 to 2.0 mg/kg/day methylprednisolone IV or IV equivalent
	
If improves to Grade 1: Taper steroids over at least 1 month and add prophylactic antibiotics for opportunistic infections Resume avelumab therapy

Pulmonary irAEs
		

Grade of Pneumonitis (NCI-CTCAE v4)
	
Management
	
Follow-up

Grade 1 Radiographic changes only
	
Consider delay of avelumab therapy Monitor for symptoms every 2 to 3 days Consider Pulmonary and Infectious Disease consults
	
Re-image at least every 3 weeks If worsens: Treat as Grade 2 or Grade 3 to 4


Grade 2 Mild to moderate new symptoms
	
Delay avelumab therapy Pulmonary and Infectious Disease consults Monitor symptoms daily, consider hospitalization 1.0 mg/kg/day methyl-prednisolone IV or oral equivalent Consider bronchoscopy, lung biopsy
	
Re-image every 1 to 3 days If improves: When symptoms return to near Baseline, taper steroids over at least 1 month and then resume avelumab therapy and consider prophylactic antibiotics If not improving after 2 weeks or worsening: Treat as Grade 3 to 4

Grade 3 to 4 Severe new symptoms; New / worsening hypoxia; life-threatening
	
Discontinue avelumab therapy Hospitalize Pulmonary and Infectious Disease consults 2 to 4 mg/kg/day methylprednisolone IV or IV equivalent Add prophylactic antibiotics for opportunistic infections Consider bronchoscopy, lung biopsy
	
If improves to Baseline: Taper steroids over at least 6 weeks If not improving after 48 hours or worsening: Add additional immunosuppression (for example, infliximab, cyclophosphamide, IV immunoglobulin, or mycophenolate mofetil)

Hepatic irAEs (reportable per section 9.3)
		

Grade of Liver Test Elevation (NCI-CTCAE v4)
	
Management
	
Follow-up

Grade 1 Grade 1 AST or ALT > ULN to 3.0 x ULN and / or total bilirubin > ULN to 1.5 x ULN
	
Continue avelumab therapy
	
Continue liver function monitoring If worsens: Treat as Grade 2 or 3 to 4

Grade 2 AST or ALT > 3.0 to ≤ 5 x ULN and / or total bilirubin > 1.5 to ≤ 3 x ULN
	
Delay avelumab therapy Increase frequency of monitoring to every 3 days
	
If returns to Baseline: Resume routine monitoring, resume avelumab therapy If elevations persist > 5 to 7 days or worsen:

	Report per section 9.3	0.5 to 1 mg/kg/day methylprednisolone or oral equivalent and when LFT returns to Grade 1 or Baseline, taper steroids over at least 1 month, consider prophylactic antibiotics for opportunistic infections, and resume avelumab therapy
Grade 3 to 4 AST or ALT > 5 x ULN and / or total bilirubin > 3 x ULN	Discontinue avelumab therapy Increase frequency of monitoring to every 1 to 2 days 1.0 to 2.0 mg/kg/day methylprednisolone IV or IV equivalent Add prophylactic antibiotics for opportunistic infections Consult gastroenterologist Consider obtaining MRI/CT scan of liver and liver biopsy if clinically warranted Report per section 9.3	If returns to Grade 2: Taper steroids over at least 1 month If does not improve in > 3 to 5 days, worsens or rebounds: Add mycophenolate mofetil 1 gram (g) twice daily If no response within an additional 3 to 5 days, consider other immunosuppressants per local guidelines
Endocrine irAEs		
Endocrine Disorder	Management	Follow-up
Asymptomatic TSH abnormality	Continue avelumab therapy If TSH < 0.5 x LLN, or TSH > 2 x ULN, or consistently out of range in 2 subsequent measurements: include T4 at subsequent cycles as clinically indicated; consider endocrinology consult	
Symptomatic endocrinopathy	Evaluate endocrine function Consider pituitary scan Symptomatic with abnormal lab / pituitary scan:	If improves (with or without hormone replacement): Taper steroids over at least 1 month and consider prophylactic antibiotics for opportunistic infections Resume avelumab therapy

	
Delay avelumab therapy 1 to 2 mg/kg/day methylprednisolone IV or by mouth equivalent Initiate appropriate hormone therapy No abnormal lab / pituitary MRI scan but symptoms persist: Repeat labs in 1 to 3 weeks / MRI in 1 month
	
Subjects with adrenal insufficiency may need to continue steroids with mineralocorticoid component

Suspicion of adrenal crisis (for example, severe dehydration, hypotension, shock out of proportion to current illness)
	
Delay or discontinue avelumab therapy Rule out sepsis Stress dose of IV steroids with mineralocorticoid activity IV fluids Consult endocrinologist If adrenal crisis ruled out, then treat as above for symptomatic endocrinopathy
	

Cardiac irAEs
		

Myocarditis
	
Management
	
Follow-up


New onset of cardiac signs or symptoms and / or new laboratory cardiac biomarker elevations (e.g. troponin, CK-MB, BNP) or cardiac imaging abnormalities suggestive of myocarditis.
	
Withhold avelumab therapy Hospitalize. In the presence of life threatening cardiac decompensation, consider transfer to a facility experienced in advanced heart failure and arrhythmia management. Cardiology consult to establish etiology and rule-out immune-mediated myocarditis. Guideline based supportive treatment as appropriate per cardiology consult.* Consider myocardial biopsy if recommended per cardiology consult.
	
If symptoms improve and immune-mediated etiology is ruled out, re-start avelumab therapy.  If symptoms do not improve/worsen, viral myocarditis is excluded, and immune-mediated etiology is suspected or confirmed following cardiology consult, manage as immune-mediated myocarditis.

Immune-mediated myocarditis
	
Permanently discontinue avelumab. Guideline based supportive treatment as appropriate per cardiology consult.* Methylprednisolone 1-2 mg/kg/day.
	
Once improving, taper steroids over at least 1 month and add prophylactic antibiotics for opportunistic infections. If no improvement or worsening, consider additional immunosuppressions (e.g. azathioprine, cyclosporine A)

*Local guidelines, or eg. ESC or AHA guidelines ESC guidelines website: https://www.escardio.org/Guidelines/Clinical-Practice-Guidelines AHA guidelines website: http://professional.heart.org/professional/GuidelinesStatements/searchresults.jsp?q=&y=&t=1001
		

## 5.6 Concomitant Medications

Concomitant medication will be evaluated at each study visit during study treatment. Concomitant medications include all vitamins, herbal remedies, over the counter, and prescription medications. Bone anti-resorptive therapy (denosumab, zoledronic acid) is permitted concurrently. ADT in the form of GnRH agonists or antagonists is permitted as part of the study as per standard of care practice. For patients on enzalutamide during screening, enzalutamide is permitted to be continued on study following progression per eligibility criteria. Enzalutamide will be able to be restarted during screening prior to study entry in patients who have had prior progression on enzalutamide per the discretion of the treating physician.

The following medications are prohibited within 2 weeks of enrollment and while on study drug, unless otherwise indicated below:

- Flutamide, bicalutamide or nilutamide;
- 5  $\alpha$ -reductase inhibitors (finasteride, dutasteride) are permitted concurrently;
- Estrogens;
- Abiraterone acetate
- Systemic glucocorticoids greater than the equivalent of 10 mg per day of prednisone unless required to treat an immune related ADR or needed as pre-treatment for an allergy to contrast;
- Androgens (testosterone, dihydroepiandrosterone [DHEA], etc.);
- All other investigational, chemotherapeutic, biologic, and radiopharmaceutical anti-cancer agents are prohibited within 4 weeks of enrollment and for the duration of study treatment
- Any herbal or complementary treatments that, in the opinion of the treating physician may increase the risk to the patient, are prohibited.

The following treatments do not require study discontinuation:

- Blood transfusions and growth factor support per standard of care and institutional guidelines;

- Steroids given at a maximum equivalent daily dose of 10 mg of prednisone;
- Pain therapy per standard of care and institutional guidelines

## 5.7 Study Drug Blinding

Not applicable, this is an open-label study

## 5.8 Randomization

Not applicable, this is a non-randomized study

## 5.9 Rationale for Selection of Dose, Regimen, and Treatment Duration

The dosing used for both the GnRH agonist and avelumab (10 mg/kg IV every 2 weeks) is derived from earlier studies described in Section 3.3.2.1.

## 5.10 Definition of Evaluable Subjects, On Study, and End of Study

Patients who consent but do not receive a dose of study drug will be replaced and will not be considered evaluable.

All subjects enrolled onto the study who receive at least one dose of avelumab will be included in the intention-to-treat analysis for the primary endpoint.

All subjects enrolled onto the study who receive at least one dose of avelumab will be evaluable for the secondary and exploratory endpoints.

Given the potential risk for delayed immune-related toxicities, safety follow-up must be performed 28 days after the last dose of avelumab administration.

The extended safety follow-up beyond 28 days after last study drug administration may be performed either via a site visit or via a telephone call with subsequent site visit requested in case any concerns noted during the telephone call.

## 5.11 Early Study Termination

This study can be terminated at any time for any reason by the PI-sponsor. If this occurs, all subjects on study will be notified as soon as possible. Additional procedures and/or follow up should occur in accordance with Section 8.8, which describes procedures and process for prematurely withdrawn subjects

# 6 STUDY DRUG

## 6.1 Names, Classification, and Mechanism of Action

Avelumab (MSB0010718C) is a fully human antibody of the immunoglobulin G (IgG) 1 isotype that

specifically targets and blocks PD-L1, the ligand for PD-1, thus removing the suppressive effects of PD-L1 on the anti-tumor CD8+ T cells. Pfizer is developing avelumab for the treatment of cancer. Avelumab is FDA-approved for treatment of adults and pediatric patients 12 years and older with metastatic Merkel cell carcinoma in the United States.

## 6.2 Packaging and Labeling

Avelumab drug product is a sterile, clear, and colorless concentrate for solution intended for intravenous (IV) infusion. The drug is presented at a concentration of 20 mg/mL in single-use glass vial containing 200 mg of avelumab.

## 6.3 Supply, Receipt, and Storage

Avelumab drug product must be stored at 2°C to 8°C until use, and it must not be frozen. Rough shaking of avelumab product must be avoided. Avelumab drug product must be diluted with 0.9% saline solution; alternatively a 0.45% saline solution can be used if needed. It is recommended that the diluted avelumab solution is used immediately. For further data on avelumab please refer to the Investigator's Brochure.

It is given as an IV in an approved chemotherapy infusion center by certified chemotherapy nurses.

## 6.4 Special Precautions for Administration

**Premedication:** In order to mitigate infusion-related reactions, a premedication with an antihistamine and with paracetamol (acetaminophen) 30 to 60 minutes prior to each dose of avelumab is mandatory (for example, 25-50 mg diphenhydramine and 500-650 mg paracetamol IV or oral). This may be modified based on local treatment standards and guidelines, as appropriate. Subjects may also be pre-medicated with steroids and/or oral or inhaled cromolyn sodium at the discretion of the provider.

**Setting:** Avelumab should be administered in a setting that allows for immediate access to an intensive care unit or equivalent environment and administration of therapy for anaphylaxis, such as the ability to implement immediate resuscitation measures. Avelumab should be given over 2 hours (-10 min/+20min). Steroids (dexamethasone 10 mg), epinephrine (1:1,000 dilution), allergy medications (IV antihistamines), bronchodilators, or equivalents, and oxygen should be available for immediate access.

**Observation period:** Following avelumab infusions, subjects must be observed for 30 minutes post-infusion for potential infusion-related reactions.

# 7 SUBJECT ELIGIBILITY

## 7.1 Inclusion Criteria

1. Neuroendocrine-like prostate cancer, based on histology OR based on clinical presentation as defined by meeting one of the two below criteria. All subjects must submit their primary tumor or metastatic biopsy pathology specimens to the Duke Cancer Institute where they will be centrally reviewed by Duke Pathology ([name]). Central Duke pathologic review is not required for screening but rather for confirmation of histologic subtype. Local pathologic review is sufficient for eligibility determination.
  - a. Criterion 1: Presence of 1 of 3 histologically proven diagnoses: **1)** Primary small cell carcinoma of the prostate, defined by classic histologic features such as small tumor cells with scanty cytoplasm, darkly stained nuclei with homogeneous chromatin pattern. The tumor cells do not form glandular structure but grow as solid sheets with frequent mitotic figures and necrosis; **2)** Intermediate atypical carcinoma of the prostate, which has histologic features distinct from small cell carcinoma or adenocarcinoma. The tumor grows as solid sheets or vague glandular structures. The tumor cells have moderate amounts of cytoplasm and centrally located, round and regular nuclei with fine, granular and homogeneous chromatin. Mitosis and necrosis are absent; **3)** mixed histology tumors of the prostate, containing both adenocarcinoma and neuroendocrine or small cell components.
  - b. Criterion 2: Presence of histologically proven adenocarcinoma of the prostate without any sign of neuroendocrine or small cell histology that is radiographically progressing despite castrate levels of testosterone (<50 ng/mL) with the following poor risk features:
    - i. Prior progression despite therapy with either abiraterone acetate and/or enzalutamide
    - ii. At least one of the following: 1) Liver metastases; 2) Bulky radiographic progression ( $\geq 2$  cm short axis lymph nodes or  $\geq 1$  cm long axis visceral metastases) combined with low serum PSA (<10ng/mL); 3) High serum LDH (>1X upper limit of normal).
2. Measurable disease as defined by modified PCWG3 using iRECIST criteria
3. Available tumor tissue for pathologic review and correlative studies. Tumor tissue (localized or metastatic) does not need to be received but rather identified and available (slides and/or blocks) to be sent to Duke.
4. Documented progressive metastatic CRPC based on at least one of the following criteria:
  - a. PSA progression defined as 25% increase over baseline value with an increase in the absolute value of at least 2.0 ng/mL that is confirmed by another PSA level with a minimum of a 1 week interval and a minimum PSA of 2.0 ng/mL. Note: If confirmed rise is the only indication of progression, a minimal starting value of 1.0 ng/mL is acceptable, unless pure small-cell carcinoma.
  - b. Soft-tissue progression based on new lesions or growth of existing soft tissue metastases.
  - c. Progression of bone disease (evaluative disease) or (new bone lesion(s)) by bone scan.
5. Cstrate levels of serum total testosterone ( $\leq 50$  ng/dl) OR ongoing documented ADT unless pure small cell prostate cancer is present.

6. Previous use of radiation to metastatic site(s) at any time prior to enrollment is allowed, provided that this site is not the only measurable disease present or unless that solitary site is progressing following radiation.
7. Patients should have received at least one line of approved chemotherapy and/or hormonal therapy
8. Previous cytotoxic chemotherapy including cisplatin, carboplatin, oxaliplatin, etoposide, docetaxel, cabazitaxel, and gemcitabine is allowed, up to 3 prior regimens.
9. Karnofsky performance status of 70 or higher.
10. Acceptable initial laboratory values within 14 days of Cycle 1 Day 1 according to the below table:

ANC	$\geq 1500/\mu\text{l}$
Hemoglobin	$\geq 9.0 \text{ g/dL}$ (prior transfusion permitted)
Platelet count	$\geq 100,000/\mu\text{l}$
Creatinine	$\leq 2.0 \times$ the institutional upper limit of normal (ULN) OR creatinine clearance $>30 \text{ ml/min}$
Potassium	$\geq 3.5 \text{ mmol/L}$ (within institutional normal range)
Bilirubin	$\leq 1.5 \times$ ULN (unless documented Gilbert's disease)
SGOT (AST)	$\leq 2.5 \times$ ULN, or $\leq 5 \times$ ULN in patients with documented liver metastases
SGPT (ALT)	$\leq 2.5 \times$ ULN or $\leq 5 \times$ ULN in patients with documented liver metastases

11. Age  $>18$
12. Highly effective contraception for male subjects with childbearing potential throughout the study and for at least 60 days after last avelumab treatment administration if the risk of conception exists.
13. Willing and able to provide written informed consent and HIPAA authorization for the release of personal health information.
14. Life expectancy of over 3 months as determined by treating physician.

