## 5 INVESTIGATIONAL PLAN

### 5.1 Study Design

This is an open label, single arm, phase 2 study of men with neuroendocrine phenotype prostate cancer to assess the safety and efficacy of avelumab 10 mg/kg IV every 2 weeks until progression or intolerable side effects. Cycles will be 4 weeks long and thus include 2 doses of avelumab. This study will be at multiple centers with the Duke Cancer Institute as the lead site. For stage 1, Duke will serve as the single site for this study. For stage 2, the study would be expanded to include additional sites

through the Department of Defense Prostate Cancer Clinical Trials Consortium (DOD PCCTC). All subjects will be followed for disease progression and death from the date that the subjects were registered to the protocol.

At radiologic progression a standard of care post-treatment progression biopsy will be collected at the discretion of the treating provider, and if proper consent is obtained, additional tissue will be collected for research tests including assessments of resistance mechanisms and immune checkpoint status. The additional research tissue will be banked in the Biospecimen Repository & Processing Core (BRPC) under Pro00080869. The study team will also pursue dual consent to BRPC Pro00035974 for future unspecified research.

Men will continue on their ADT used at entry into study per investigator with subsequent changes made per investigator. Men not on ADT at time of entry due to being purely SCPC can remain off ADT. Men with SCPC on ADT at study entry can remain on ADT per investigator while all men with mixed histologies should remain on active ADT during trial participation.

Men will be allowed to receive palliative radiation to any disease site indicated by the treating physician at any time before or during the study, provided that another untreated site of measureable disease is present at baseline.

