agonists or antagonists. ADT will continue throughout all cycles. If patient has pure SCPC they do not need to be started on ADT but are allowed to continue per treating provider if already on ADT. Concurrent enzalutamide is permitted.

9. **Study Treatment (Avelumab):** Avelumab will be administered at 10 mg/kg IV every 2 weeks. One cycle is 2 infusions (4 weeks).
10. **Tumor imaging:** Bone scan, and either CT or MRI scans of the chest, abdomen, and pelvis will be performed to assess disease status at baseline as well as every 8 weeks or at treatment discontinuation (if imaging did not occur within 6 weeks of visit ) as well as whenever disease progression is suspected, to confirm partial or complete response. NaF-PET/CT may be used in place of bone scan and CT in select cases. In all cases, the same imaging modality should be used throughout the study on individual subjects. Baseline tumor imaging must be performed within 35 days of cycle 1 day 1. MRI brain should be done in all subjects at baseline if indicated clinically and should be followed every 8 weeks with the other scans if metastasis(es) are found or if disease progression is suspected. Allowable window for tumor assessment imaging studies is +/- 7 days. Subjects removed from therapy for any reason other than disease progression will continue to be followed for radiographic progression until additional treatments are started, when available.
11. **Post-Progression Biopsy:** An optional standard of care post-treatment progression biopsy will also be collected and additional tissue for research will be banked in the Biospecimen Repository & Processing Core (BRPC) under Pro00080869 for future research on resistance mechanisms including assessment of immune checkpoint status.
12. **Physical Examination:** Examination of major body systems. It does **not** need to be done cycle 1, day 1 if performed within the last 7 days.
13. **Adverse Events:** Subjects must be followed for adverse events from the first day of study treatment until 28 days after the last dose of study treatment, or until all serious or study drug-related toxicities have resolved or are determined to be “chronic” or “stable”, whichever is earlier. Serious adverse events should be monitored and reported from the time the patient starts study drug treatment as described in the protocol.

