### 11.4 Treatments

Avelumab with ADT (unless pure SCPC present) will start on cycle 1 day 1 and continue every 2 weeks until progression or unacceptable toxicity.

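### For men with intermediate atypical or mixed histology, inclusion 5 lets ongoing ADT stand in for a castrate testosterone, so a response to falling testosterone could count as an avelumab response

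*Combined protocol and SAP*

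**What the plan says.** Inclusion 5 in section 7.1, repeated in the synopsis, is met by a total testosterone of 50 ng/dl or less "OR ongoing documented ADT unless pure small cell prostate cancer is present". Either branch is enough.

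Inclusion 4 requires "Documented progressive metastatic CRPC based on at least one of the following criteria". The criteria listed are a PSA rise, soft-tissue progression and bone progression. None mentions a testosterone level, or says that the progression must have occurred on ADT.

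Inclusion 1 has two routes. Criterion 2 (adenocarcinoma without neuroendocrine histology) requires disease "radiographically progressing despite castrate levels of testosterone (<50 ng/mL) with the following poor risk features", the first of which is "Prior progression despite therapy with either abiraterone acetate and/or enzalutamide". Criterion 1 is histological. It covers small cell carcinoma, intermediate atypical carcinoma and "mixed histology tumors of the prostate, containing both adenocarcinoma and neuroendocrine or small cell components", and has no castration condition of its own.

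On the timing of ADT, section 5.1 says "Men will continue on their ADT used at entry into study per investigator with subsequent changes made per investigator". The synopsis agrees, and footnote 8 to the schedule has men already on ADT continue it. Section 11.4 says "Avelumab with ADT (unless pure SCPC present) will start on cycle 1 day 1".

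**The concern.** The trial has no control arm and its primary variable is CR or PR (11.5.1). Any tumour shrinkage in an enrolled man is credited to avelumab. That is safe for hormonal effects only if men with a hormone-sensitive component are already castrate at baseline. Section 3.1 says treatment begins with ADT because most of these cancers are mixed with adenocarcinoma, so the protocol itself expects that component to matter.

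A man with mixed or intermediate atypical histology who progressed while inadequately suppressed, or whose ADT has not yet brought testosterone down, can satisfy the listed tests in item 4 and the ADT branch of item 5. The same ADT can satisfy item 7, which accepts hormonal therapy as the prior line. If his testosterone then falls on study and his tumour shrinks by 30%, he is one of the five responders needed. The plan has no rule for attributing or setting aside such a response.

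**Working it through.** **Which men are affected**

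| Group | Castrate testosterone required? |
|---|---|
| Criterion 2 | Yes, in words, with no ADT alternative, plus prior progression on abiraterone and/or enzalutamide |
| Criterion 1, pure small cell | Exempt by design |
| Criterion 1, intermediate atypical or mixed | Only through item 5, where ongoing ADT can replace it |

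The gap is the third row.

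**Reproducing the design (11.1)**

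Inputs: stop if 1 or fewer of 18 respond; otherwise add 26 men; promising if 5 or more of 44 respond; null rate 5%, alternative 20%.

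P(promising) = sum over x = 2 to 18 of P(X1 = x) × P(X2 ≥ 5 − x), with X1 ~ Bin(18, p) and X2 ~ Bin(26, p).

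- p = 0.05: 0.0495 (stated 0.05)
- p = 0.20: 0.8806 (stated 88%)
- P(X1 ≤ 1) at p = 0.05: 0.7735 (stated 0.77)

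The plan's figures reproduce and are not in dispute.

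**Adding men who are not castrate at baseline**

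Assumptions, none of them in the documents: the true avelumab rate is 5%; exactly m of the 44 men are not castrate at baseline; each responds to castration with probability q, independently of avelumab. An affected man then responds with probability 1 − 0.95(1 − q):

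- q = 0.30: 1 − 0.95 × 0.70 = 0.335
- q = 0.50: 1 − 0.95 × 0.50 = 0.525

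If the m men fall at random among the 44, the chance that k are in stage 1 is C(18,k)·C(26,m−k)/C(44,m). For each k, X1 is the sum of Bin(18 − k, 0.05) and Bin(k, 0.335 or 0.525). X2 is built the same way for the remaining 26, and the decision rule is unchanged.

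| m | k in stage 1 | Weight | P(promising), q = 0.30 | P(promising), q = 0.50 |
|---|---|---|---|---|
| 1 | 0 | 0.591 | 0.0662 | 0.0774 |
| 1 | 1 | 0.409 | 0.0798 | 0.1000 |
| **1** | **average** | | **0.072** | **0.087** |
| 2 | 0 | 0.344 | 0.0844 | 0.1093 |
| 2 | 1 | 0.495 | 0.1048 | 0.1508 |
| 2 | 2 | 0.162 | 0.1190 | 0.1753 |
| **2** | **average** | | **0.100** | **0.140** |

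Widening q to 20%-80% gives 0.064 to 0.109 for one man and 0.082 to 0.211 for two. With m = 0 the figure stays at 0.0495.

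**The case against.** **CRPC is required.** Inclusion 4 says so, and the synopsis and 11.3 repeat it. A man who has just begun ADT is not castration-resistant in the ordinary sense, and most investigators would not enrol him. This stands as a reason to expect few affected men. It does not close the gap, because the criteria by which item 4 documents CRPC never refer to testosterone.

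**Testosterone is followed on study.** It is drawn at screening, on Day 1 of each cycle and at least every 4 weeks. A man who enters above the limit and then falls would be visible in the data. This also stands. A castration response would not be hidden, but under the present rules it would still be counted.

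**Stronger readings the documents do not support.**

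- *Every man without pure small-cell disease is exposed.* Criterion 2 men must already be progressing despite castrate testosterone and after abiraterone and/or enzalutamide. Criterion 2 prints its limit in ng/mL where item 5 uses ng/dl, a 100-fold difference that also needs reconciling, but its words still require castration.
- *Castration begins with avelumab.* Section 11.4 can be read that way, but it is one sentence against the synopsis, 5.1, footnote 8 and a schedule that marks ADT at screening. The clause in footnote 8 "If patient has pure SCPC they do not need to be started on ADT" concerns pure small-cell disease only and does not say that others start. ADT first given on cycle 1 day 1 would not be ongoing for item 5.
- *The false-positive rate could reach a third.* A 10% non-castrate share with 50% responding to castration gives an overall rate of 0.90 × 0.05 + 0.10 × 0.525 = 0.0975, and a 0.34 chance of declaring promise. Nothing in the documents supports a share that high in a trial that requires CRPC.

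**Conclusion.** The point holds for Criterion 1 men with intermediate atypical or mixed histology. For them, eligibility does not guarantee castration at baseline, and the primary analysis has no protection if it is absent.

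The 5% false-positive rate becomes about 7% to 9% with one affected man in 44, and about 10% to 14% with two. These figures rest on an assumed avelumab rate of 5% and an assumed 30% to 50% response to castration. The number of affected men is unknown and probably small, and with none the design performs as stated. This is an inexpensive safeguard worth adding, not evidence that the result will be biased.

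The conflict between 11.4 and the other passages on ADT is a separate drafting matter.

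**What to change.** 1. In inclusion 5 (synopsis and 7.1), apply the protocol's own limit of 50 ng/dl or less to the screening testosterone of every man except those with pure small-cell disease, so that documented ADT no longer substitutes for it.
2. In 11.5, add a sensitivity analysis that reports the response rate with and without any enrolled man whose screening testosterone exceeded the limit. This also covers men enrolled before the amendment.
3. Reconcile 11.4 with 5.1, the synopsis and footnote 8 on when ADT starts. Which timing is intended is for the sponsor to state.

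The cost is amendment wording and one extra line in the results. Testosterone is already drawn at screening (8.1 and the schedule), so no new test is needed. The small downside is that an occasional man on ADT who is not yet castrate is delayed or not enrolled.
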